## 303 **2.4 Screen Failures**

304 Individuals who do not initially meet study eligibility requirements may be rescreened one more time at a  
305 later date per investigator discretion.

306 **2.5 Lead-in Period**

307 All participants will complete the Lead-in Period as an outpatient for approximately 16 days. The Lead-in  
308 Period may begin the same day the screening visit is completed or within 4 weeks after informed consent  
309 is signed. The lead-in period will last at least 16 days and no more than 21 days.

310 At the initiation of the Lead-in Period (CIQ 1.5/ Humalog Training Visit), participants will switch from  
311 their current Control-IQ system to the study pump (Control-IQ 1.5 technology), study sensor, and study-  
312 provided Humalog (insulin lispro injection). Training will be provided by qualified study staff on the  
313 study pump, the study CGM sensor, the study glucose meter, and the study ketone meter. The study  
314 investigator may adjust insulin delivery profile settings as indicated.

315 During the lead-in period, each participant will perform one meal and exercise challenge to determine a  
316 baseline using Humalog and Control-IQ 1.5. Those day and overnight periods will be analyzed separately.  
317 Procedures are described in section 5.1. A minimum of 48 hours will occur between all challenges for  
318 each participant.

319 After 16 days (and up to 21 days), the participant will have a visit. System use will be assessed and to  
320 proceed to the Treatment Period, it is necessary that a participant used the Control-IQ system, with at  
321 least 85% of system use (active closed loop) reported over the time of the lead-in period (ie, minimum of  
322 85% of 14 days).

323 The lead-in period data collection may be repeated if this threshold is not met.

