361 CGM related to mobile data access or remote monitoring, but will be instructed not to use any third-party  
362 components for this purpose. For pediatric participants, the parent/caregiver will use the Dexcom Follow  
363 app (with push notifications turned on) for the duration of the study.

364 The t:connect mobile app from Tandem Diabetes Care will not be available for use during the trial, and  
365 will not pair to the study pump.

366 Study staff will discuss with the participant that routine contact is required and will make arrangements  
367 with the participant for the contacts. If the participant cannot be reached, the participant's other contact  
368 methods will be utilized, including the emergency contact. Participants who are not compliant with the  
369 arranged contacts on two separate occasions may be discontinued at the discretion of the investigator.

370 Following the CIQ 1.5/Lyumjev Training Visit, participants will use the study pump and the  
371 investigational insulin for ~90 days during the Treatment Period.

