- 1029 • Socio-economic factors (income, education, and/or insurance status)
- 1030 • Diabetes duration
- 1031 • HbA1c
- 1032 • BMI
- 1033 • Total daily insulin
- 1034 • Prior severe hypoglycemia and DKA events
- 1035 • Baseline CGM metrics

1036 **8.10 Additional Tabulations and Analyses**

1037 The following data will be tabulated at baseline and at or over 13 weeks

- 1038 • Insulin metrics (units/kg): total daily insulin, total daily basal insulin, total daily bolus insulin  
1039 (plus total daily manual bolus, total daily automated bolus)
- 1040 • Weight
- 1041 • Number and type of infusion set reactions

1042 **8.11 Device Issues**

1043 The following tabulations will be performed with respect to device issues:

- 1044
  - Reported device issues according to type of issue

1045 **8.12 Planned Interim Analyses**

1046 No formal interim analyses are planned.

1047 **8.13 Subgroup Analyses**

1048 Results will be tabulated according to age group, HbA1c, and total daily insulin. Additional subgroups  
1049 will be defined in the Statistical Analysis Plan.

1050 **8.14 Multiple Comparison/Multiplicity**

1051 Safety event endpoints will not be corrected for multiple comparisons. For CGM, HbA1c, and PRO  
1052 endpoint analyses, the false discovery rate will be controlled using the adaptive Two Stage Group  
1053 Benjamini-Hochberg (TST GBH) method.

1054 **8.15 Analysis of Meal and Exercise Challenges**

1055 The meal and exercise challenges will be analyzed with the same CGM metrics and safety outcomes  
1056 above to be tabulated during, 2 hours after and overnight for each challenge, and will be detailed in the  
1057 statistical analysis plan. Separate analysis will be conducted for each type of challenge.

1058

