### 369 **10.2 Infusion Site Reactions**

370 The following metrics will be tabulated separately for the lead-in and treatment periods.

- 371 • Number of infusion site reactions (number of events and number of participants with  $\geq 1$   
372 event).
- 373 • Number of infusion site reactions resulting in an adverse event.
- 374 • Number of infusion site reactions resulting in study discontinuation.
- 375 • Number of infusion site reactions per participant
- 376 • Number of infusion site reactions per study week
- 377 • Total number of each type of reaction (erythema, induration, site pain, pruritis, edema)  
378 overall and by reaction severity (mild/moderate or severe). The total number of events  
379 and number of participants with  $\geq 1$  event will be tabulated.

TL1 SAP V4.0 08-22-23

380 The following metrics will be tabulated in the treatment period and tabulations will be stratified  
381 by reaction type (erythema, induration, site pain, pruritis, edema). Tabulations will further be  
382 stratified by pediatric and adult participants and by reaction severity (mild/moderate or severe).

- 383 • Duration of infusion site reaction
- 384 • Timing of reaction relative to Lyumjev insulin administration
- 385 • Location of infusion site reaction

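### SAP 10.2 gives site reactions by type and severity as raw counts over a 16–21 day Humalog lead-in and a 91–98 day Lyumjev period, so at unchanged risk event counts on Lyumjev are 4.3 to 6.1 times higher from period length alone

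*SAP*

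**What the plan says.** SAP 10.2 opens its main list with "The following metrics will be tabulated separately for the lead-in and treatment periods". The list contains:

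- the overall count, "Number of infusion site reactions (number of events and number of participants with" at least one event;
- reactions that became adverse events, and reactions that led to discontinuation;
- reactions per participant;
- "Number of infusion site reactions per study week";
- "Total number of each type of reaction (erythema, induration, site pain, pruritis, edema"), overall and split into mild/moderate or severe, again as events and as participants with at least one.

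Only the per-study-week row refers to time, and it is not broken down by type or severity. The protocol's counterpart in section 8.10 is "Number and type of infusion set reactions", with no rate.

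On period length, Protocol 2.5 says "The lead-in period will last at least 16 days and no more than 21 days", and adds "The lead-in period data collection may be repeated if this threshold is not met". Protocol 3.1.1 describes use of the "investigational insulin for ~90 days during the Treatment Period", and the visit table in Protocol 3.2 sets the final visit at 91 to 98 days.

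**The concern.** The two columns of the table cover periods that differ about five-fold in length. A raw count grows with time at risk, so the type and severity rows would show more pain, erythema, induration and so on under Lyumjev even if the two insulins were equally well tolerated. This would be so even if reactions were looked for in the same way in both periods.

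It matters because local tolerability is a risk the protocol singles out. Protocol 1.3.1.8 promises careful monitoring of infusion site reactions, and the synopsis names them within a secondary safety endpoint. The lead-in is the only period for which the SAP tabulates site reactions on Humalog. A reader who wants to know whether a given type of reaction is more or less frequent on Lyumjev will go to these rows, and as laid out they do not answer that directly.

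The rates planned elsewhere do not fill the gap. The rates per 100 person-years in SAP 6.1 and 8.1 cover the key safety endpoints, and the rate in SAP 8.2 covers adverse events in the treatment period. Under Protocol 6.2.2 and 6.2.5, a mild or moderate infusion set reaction that was not treated is not a reportable adverse event, so it does not enter those rates.

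**Working it through.** The plan states no figure on this point, so there is nothing to reproduce.

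**Inputs.** Lead-in length L = 16 to 21 days (Protocol 2.5). Treatment length T = 91 to 98 days (Protocol 3.2). The reaction rate h per participant-week is not given in the documents. It is assumed, constant over time and the same on both insulins, and shown over a range.

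**Event counts.** Expected events are h × weeks × participants, so h cancels and the ratio is T/L:

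- 91/21 = 4.33
- 98/21 = 4.67
- 91/16 = 5.69
- 98/16 = 6.13

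This holds for each reaction type and each severity. Two things would lower it:

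- Dropout. If 40 of 200 starters left midway (an assumption), the ratio is (160×91 + 40×45.5)/(200×21) = 3.9 to (160×98 + 40×49)/(200×16) = 5.5.
- A repeated lead-in. If both lead-ins were counted (2×16 = 32 to 2×21 = 42 days), the ratio for those participants is 91/42 = 2.2 to 98/32 = 3.1.

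**Participants with at least one event.** With a common rate h, P = 1 − exp(−h × days/7).

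| Assumed h per participant-week | 21 vs 91 days | Ratio | 16 vs 98 days | Ratio |
|---|---|---|---|---|
| 0.005 | 1.5% vs 6.3% | 4.2 | 1.1% vs 6.8% | 6.0 |
| 0.01 | 3.0% vs 12.2% | 4.1 | 2.3% vs 13.1% | 5.8 |
| 0.05 | 13.9% vs 47.8% | 3.4 | 10.8% vs 50.3% | 4.7 |
| 0.1 | 25.9% vs 72.7% | 2.8 | 20.4% vs 75.3% | 3.7 |
| 0.2 | 45.1% vs 92.6% | 2.1 | 36.7% vs 93.9% | 2.6 |
| 0.5 | 77.7% vs 99.8% | 1.3 | 68.1% vs 99.9% | 1.5 |

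The ratio is always below T/L and falls as reactions become common. Letting participants differ in their underlying rate (gamma frailty, shape 0.5) gives 3.8 to 5.3 at h = 0.01, 2.3 to 2.8 at 0.1 and 1.5 to 1.7 at 0.5.

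**With a denominator.** Take 160 participants and h = 0.05. Raw counts are 160 × 0.05 × 3 = 24 against 160 × 0.05 × 13 = 104 events (21 and 91 days), or about 18 against 112 (16 and 98 days). Per study week, both periods show 160 × 0.05 = 8.0, a ratio of 1.0.

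**The case against.** The strongest reply is that this is a matter of presentation. SAP 10 offers summary statistics only. No test, interval or success criterion compares site reactions between periods. The overall count already has a per-week row. Every event row within a period shares the same exposure and the period lengths are stated, so a reader can rescale event counts by hand. The distortion runs against Lyumjev, so it gives no false reassurance. All of this stands, and it limits the point to interpretation. It does not remove it: the proportions with at least one event cannot be rescaled by a constant, and no person-time for the lead-in is defined (SAP 6.1 counts from the start of treatment). The SAP itself puts such comparisons on a weekly scale, in its own per-week row and for infusion set changes in SAP 10.5.

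A reader might infer three stronger things that the documents do not support:

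- **That participants with at least one reaction are also inflated 4 to 6 times.** That needs rare reactions, and no document gives a reaction rate.
- **That no Humalog–Lyumjev comparison is possible.** The per-study-week row allows an overall one if it is a rate. Its wording could also mean a count for each week of study.
- **That this table will go into labeling.** The documents say the study supports labeling, not which table will be used.

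A further objection is that a denominator does not make the periods fully comparable. This is correct. The weekly site contact and the photographs of the first two sets removed (Protocol 3.1.4), and the site inspection or photograph at 3 days, 1 week and 2 weeks (Protocol 3.2.1), are set out for the treatment period. The visit schedule shows no contact between the Humalog and Lyumjev training visits. Protocol 5.1 adds contacts around the challenges but does not describe them as site inspections. A rate also assumes a roughly constant risk over time.

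**Conclusion.** The point holds for the rows without a denominator. Event counts by type and severity would be 4.3 to 6.1 times higher on Lyumjev at unchanged risk, from period length alone. This rests on the stated period lengths, full follow-up, a single lead-in and a constant rate. Participants with at least one event would be inflated too, by about 4 to 6 times if reactions are rare (assumed 0.01 per participant-week or less) and by 1.3 to 2.6 times at an assumed 0.2 to 0.5 per participant-week. The overall per-week row is a partial safeguard. Because the table is descriptive, no error rate is affected. The consequence is that differences by type and severity can be misread.

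**What to change.** In SAP 10.2:

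1. Next to the raw counts, report each reaction type and severity in both periods as events per participant-week (or per 100 participant-weeks). A figure per infusion set worn is an optional addition, since set changes are already handled in SAP 10.5.
2. Define person-time for the lead-in and say how a repeated lead-in counts. SAP 6.2 settles this for CGM metrics by using the most recent lead-in, but 10.2 is silent.
3. State that per study week is a rate, and give its denominator.
4. Label every row of participants with at least one event with the exposure time in each period. If an equal-window row is added, note beside it that site inspection is more intensive in the first weeks of Lyumjev than in the lead-in, so neither a rate nor an equal window removes that difference.

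Confidence intervals are optional. No new data are needed. SAP version 4.0 records follow-up as complete, so the cost is a person-time definition and minor extra table work.

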### 386 **10.3 Open-Loop Basal Rates**

387 Participants will be split into subgroups based on whether the open-loop basal rate exceeds  $\geq 3$   
388 U/hr for at least part of the day during the lead-in period. Summary statistics for mean glucose,  
389 time in range 70-180 mg/dL, time in range 70-140 mg/dL, time  $> 180$  mg/dL, time  $> 250$  mg/dL,  
390 glucose SD, glucose CV, time  $< 70$  mg/dL, and time  $< 54$  mg/dL will be reported within these  
391 subgroups. A listing of outcomes in each period will be provided for participants who set the  
392 open-loop basal rate to  $\geq 3$  U/hr.

### 393 **10.4 Pump Settings**

394 Summary statistics for the profile basal rate (U/day), carb ratio, and insulin sensitivity factor  
395 (ISF) will be tabulated for week 1, week 13, and the change from week 1 to week 13. If different  
396 carb ratio or ISF settings are used within a given week, then a weighted average will be  
397 calculated based on the length of time each setting was used.

### 398 **10.5 Infusion Set Changes**

399 Appropriate summary statistics for the interval between infusion set changes will be tabulated.  
400 The intervals between infusion set changes will be categorized and the number and percentage in  
401 each category will be tabulated separately for the lead-in and treatment periods. Tabulations will  
402 be reported for the overall cohort and separately for pediatric and adult participants.

403 The mean number of infusion set changes per week will be calculated on a participant level and  
404 compared between the Humalog and Lyumjev periods using a linear mixed model with clinical  
405 site included as a random site effect. If residuals are skewed, then a transformation or non-  
406 parametric method will be used.

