### 3.1 CIQ 1.5/ Lyumjev Training Visit

326 At the end of the Lead-in Period, participants will have a clinic visit at which their use of the CIQ 1.5  
327 system with Humalog will be assessed. Participants who successfully used the system with at least  
328 85% of system use (active closed loop) will undergo device training with Lyumjev in the study pump.

329 A blood sample (venipuncture or fingerstick) will be obtained to send to the central laboratory for  
330 HbA1c measurement.

331 Participants will receive supplies for blood glucose and ketone testing. QC testing will be performed on  
332 the meters before they are dispensed.

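### SAP 10.5 compares infusion set changes per week between a 16–21 day and a 91–98 day period without a counting rule, so unchanged wear can appear as a difference

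*SAP*

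**What the plan says.** SAP 10.5 plans two things. The first is descriptive: "Appropriate summary statistics for the interval between infusion set changes will be tabulated", with categorised intervals shown separately for lead-in and treatment. The second is a test. "The mean number of infusion set changes per week will be calculated on a participant level and" then "compared between the Humalog and Lyumjev periods using a linear mixed model with clinical" "site included as a random site effect". No participant effect is named, although each participant contributes a value from each period. No window is given, and nothing says whether the set placed at a switch visit counts or how an interval cut off by the next visit is handled.

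The two periods differ greatly in length. Protocol 2.5 states: "The lead-in period will last at least 16 days and no more than 21 days". Protocol 3.1.1 describes use of the "investigational insulin for ~90 days during the Treatment Period", and the visit table in Protocol 3.2 puts the final visit at 91 to 98 days.

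On what happens at the switches, Protocol 2.5 has participants move from "their current Control-IQ system to the study pump (Control-IQ 1.5 technology") and start study-provided Humalog. Protocol 3.1 says that those who pass the lead-in "will undergo device training with Lyumjev in the study pump". Neither passage mentions a new infusion set.

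**The concern.** A change of pump, or of the insulin in it, makes a new infusion set at the visit likely. If both periods start with a new set, the count in a period is its length divided by mean wear, plus a roughly constant start-and-end offset. Dividing by about 2.3 to 3 weeks in one period and 13 to 14 in the other leaves very different amounts of that offset in the two rates. The comparison would then show a difference even when wear had not changed.

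The sign depends on the counting rule. If the visit set is not counted, Lyumjev appears to need more changes. If it is counted, Lyumjev appears to need fewer, and a real increase could be masked. Infusion site reactions are a stated concern with this insulin (Protocol 1.3.1.8), so a reader may give weight to either result.

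**Working it through.** The documents give no figure for this comparison, no wear time and no variance, so there is nothing to reproduce.

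**From the documents:** lead-in T₁ = 16 to 21 days (Protocol 2.5); treatment T₂ = 91 to 98 days (Protocol 3.2); 160 completers (SAP 4).

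**Assumed:** a new set at each switch; mean wear μ of 2 to 3.5 days; within-person CV of wear 0.27 (0.2 to 0.4 in some runs); SD of individual change 0 or 0.5 per week; two-sided 0.05. SAP 13 lists no multiplicity group that contains this comparison.

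**Expected count.** For a process started at a new set, E[N(T)] ≈ T/μ − 0.5 + CV²/2. With CV = 0.27, CV²/2 = 0.036. The offset is −0.464 if the visit set is not counted and +0.536 if it is.

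**Rates per week at μ = 3 days (true rate 7/3 = 2.33):**

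| Visit set | 16 days | 21 days | 91 days | 91 minus 16 | 91 minus 21 |
|---|---|---|---|---|---|
| Not counted | 2.131 | 2.179 | 2.298 | +0.17 | +0.12 |
| Counted | 2.568 | 2.512 | 2.375 | −0.19 | −0.14 |

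For example, 7 × (16/3 − 0.464)/16 = 2.131 and 7 × (91/3 − 0.464)/91 = 2.298.

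**General form.** The difference is 7 × offset × (1/T₂ − 1/T₁), in which μ cancels. With T₂ = 98 the results are +0.17 and −0.20 (T₁ = 16), and +0.12 and −0.14 (T₁ = 21), so the 91 to 98 day window hardly matters. Simulation over mean wear of 2 to 3.5 days gives +0.11 to +0.17 and −0.13 to −0.20.

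**Relative size.** The true rate runs from 7/2 = 3.5 to 7/3.5 = 2.0 per week. With a 16-day lead-in the artefact is 0.167/3.5 = 5% to 0.193/2.0 = 10%. With 21 days it is 0.119/3.5 = 3% to 0.138/2.0 = 7%.

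**How often it reaches p < 0.05 with no true mean change (N = 160):**

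- Paired test: 93 to 100% with no individual change in wear, and about 64 to 99% with an SD of change of 0.5 per week.
- Site-only model as written, approximated by an unpaired test with no site variance: about 0 to 97% with an SD of change of 0.5. With mean wear 3 days, lead-ins of 16 to 21 days and no individual change, it is 90 to 100% at a between-person wear SD of 0.3 days, 40 to 93% at 0.6 days, and 1 to 4% at 1.0 day.

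The low rates come from ignoring the pairing. The bias in the estimate is unchanged, and the same insensitivity would hide a real change.

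**Other windows.** Starting the day after the visit, as SAP 6.2.2 and 6.4 do for other metrics, still leaves about +0.07 to +0.12 per week. Windows not tied to a new set show essentially no bias (within about 0.006).

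**Remedies, with wear unchanged:**

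- Equal-length windows from the same anchor: bias about 0, paired rejection 2 to 8%.
- Changes after the visit insertion divided by time to the last change: at μ = 3, 2.37 (16 days) against 2.34 (91 days), a residual of about −0.02 to −0.03 per week. It reached about −0.06 at a within-person CV of 0.4.

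**The case against.** The strongest reply is that the plan prescribes none of this. Neither document says that a set is replaced at either switch, and SAP 10.5 does not fix a count divided by calendar days. Its preceding paragraph works with intervals, so a rate built from completed intervals is equally open. If the CGM rule in SAP 6.2 (last 16 days of the lead-in) were borrowed, longer lead-ins would not start at a new set. All of that stands. The bias is conditional and its direction is open.

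A reader might infer that the unequal periods by themselves guarantee a false significant result. The documents do not support that: it needs the inferred new set and a calendar-time count, and the site-only model as written may reject almost never.

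A reader might also note that SAP version 4.0, which added the set-change analyses, is dated after follow-up was complete, and infer that the counting rule was left open so that a result could be chosen. Nothing in the documents shows that.

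Nor do the documents call change frequency a tolerability endpoint. Site reactions (SAP 10.2) and occlusion alarms prompting a set change (SAP 10.1) cover tolerability more directly, and the interval tables in SAP 10.5 would let a reader see whether wear shifted.

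What remains is that the natural count-per-week readings anchored at the switch are biased, and the text does not exclude them.

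**Conclusion.** The point holds in conditional form. SAP 10.5 leaves the metric undefined across periods that differ about four- to six-fold in length. Given a new set at each switch and division by calendar time, unchanged wear can show about +0.11 to +0.17 changes per week (visit set not counted) or −0.13 to −0.20 (counted).

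The size of the bias depends on the period lengths and little on wear time. The chance of a significant result depends heavily on assumptions: the between-person spread in wear, the SD of individual change, and whether the analysis is paired. The new set at each switch is a reasonable inference, not document text.

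The comparison sits under the SAP's additional analyses with no decision rule, and it affects no key safety endpoint. Priority is low.

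**What to change.** In SAP 10.5:

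- **Primary comparison.** For each participant, compare the lead-in with the same number of days from the Lyumjev switch. State the anchor, whether the visit insertion counts, and the end of the window, and apply the same rule in both periods.
- **Secondary analysis.** Report the full-period rate as changes after the visit insertion divided by time from that insertion to the last change, noting the residual bias of about −0.02 to −0.03 per week.
- **Model.** If a paired comparison is intended, name a participant effect. This affects precision, not the bias.

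The cost is a few sentences and a few lines of code on pump data already downloaded. The downside is that later Lyumjev data do not enter the primary comparison, so a change in wear that emerges only later would show in the secondary analysis alone.
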